3.0 RESEARCH SUBJECT SELECTION AND ELIGIBILITY

Setting

Radiation Therapy Departments of the Seidman Cancer Center at the University Hospitals main campus, satellite community facilities, and MetroHealth Cancer Center.

Population

The sample will consist of family CGs of individuals with HNC, NSCLC, rectal, anal, and esophageal cancer. In this study, a family CG is defined as an adult who is providing daily assistance and/or emotional support to the individual with cancer as identified by the patient. The sample will be drawn from the population of patients at the Cancer Center. Data obtained from the Cancer Center tumor registry show that 403 adult patients with new diagnoses of HNC, rectal, anal, and esophageal cancer (all stages) and stage III NSCLC cancer were evaluated in 2017. Demographic characteristics were: 62.5% male, 37.5% female, 82.4% White, 16.4% Black, and a mean age of 64 years. Fifty-seven percent underwent radiation therapy.

The extension period will include family CGs and patients recruited from MetroHealth, an academic medical center and Cuyahoga County's safety-net health system. It is located in the City of Cleveland, which is racially and ethnically diverse (49% Black, 40% White, 11.9% Hispanic).

Sampling Procedure and Group Assignment

A convenience sample of family CGs will be used.

Inclusion criteria for patients are: (1) 18 years of age or older. (2) Diagnosis of stage I, II, III

cancers of the rectum and anus, stage I, II, III, IVa esophagus; stage II-III NSCLC (excluding those receiving SBRT due to short treatment course); and stage I – IV A/B head/neck (tongue, gum, oral cavity, nasopharynx, oropharynx, hypopharynx, parotid, or larynx). Stage IV A/B will be allowed for HNC and stage IVa for esophagus as the intent of therapy is curative. (3) Has an identified family CG who is willing to participate.

Inclusion criteria for CGs are: (1) 18 years of age or older; (2) family member or friend of an adult patient described above; and (3) identified by the patient as his/her primary CG, who is providing daily assistance and/or emotional support.

Exclusion criteria are: Patients who do not have a caregiver will be excluded. CGs of patients who are receiving hospice care will be excluded because of the patient's poor prognosis and multiple issues associated with end-of-life care. CGs who are themselves undergoing active cancer treatment will be excluded (hormonal treatment allowed).

Projected Enrollment

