During the extension period, qualitative interviews will be conducted either in-person, by phone, or using UH Zoom based on caregiver preference. The interviewer will follow the interview guide, adding prompts and follow-up questions as appropriate. Interviews will last approximately 30 to 45 minutes. Interviews will be recorded and the data file will be uploaded to UH Box for storage.

Table 4. Study Measures

VARIABLE	INSTRUMENTS	TIME			
		T1	T2	T3	T4
CG Outcomes					
CG Anxiety	Patient Reported Outcomes Measurement Information System (PROMIS) ⁹⁵ Anxiety Short Form 7a	X	X	X	X
CG Depression	PROMIS ⁹⁵ Depression Short Form 8b	X	X	X	X
CG HRQOL	PROMIS ⁹⁵ Global Health Scale v.1.0/1.1	X	X	X	X
CG Fatigue	PROMIS ⁹⁵ Fatigue Short Form 7a	X	X	X	X
Patient Outcomes					
HRQOL	FACT-C, v. 4, ⁹⁶ FACT-E, v. 4, ⁹⁷ FACT-H&N, v. 4, ⁹⁸ and FACT-L, v. 4 ^{104, 105}	X	X	X	X
Interrupted radiation treatment course (total number of missed days from treatments)	Radiation Therapy PT treatment record		X		
Healthcare Utilization Outcomes					
Unplanned hospital admission	Hospital record		X	X	X
Unplanned emergency room visits	Hospital record		X	X	X
Unplanned intravenous fluid use	Hospital record (number of liter bags used)		X	X	X
Cognitive Mediator					
CG self-efficacy for caregiving	CG Inventory ⁹⁹	X	X	X	X
	Investigator-constructed self-efficacy scale for managing side effects & specific skills	X	X	X	X
Potential Moderators (Covariates)					
Patient Illness Factors (Stage; time since diagnosis; treatment type, e.g., concurrent chemotherapy; HPV status in HNC and anal cancer)	PT medical record	X			
Use of palliative care services	PT medical record	X	X	X	X
PT Performance Status	ECOG Performance Status ^{100,101} (patient)	X	X	X	X
Care Demands (hours/week spent caregiving)	Interview questions (CG)	X	X	X	X
Demographic characteristics (race, marital status, employment status, health insurance, socioeconomic status)	Interview questions (CG and PT)	X			
Use of mental health interventions (support group participation, social work and/or psychologist involvement)	Interview questions (CG and PT)	X	X	X	X
Financial toxicity	COST-FACIT (version 2)		X		X
Social support	MOS		X		

Note. PT = Patient; CG = Caregiver; ECOG = Eastern Cooperative Oncology Group; ADLs = Activities of daily living. CG age, CG gender, and PT cancer type will be used in the minimization stratified randomization technique. Number/types of care demands will be collected as descriptive data.

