6.0 STATISTICAL ANALYSIS

6.1 Primary and secondary endpoints.

The primary endpoint is difference in caregiver anxiety between the intervention and control groups at 20

weeks post-radiation treatment. Secondary endpoints are caregiver anxiety at the end of radiation treatment and 4 weeks post treatment; caregiver depression, HRQOL, and fatigue at the end of treatment and 4 weeks post-treatment; and patient HRQOL at the end of treatment and 4 weeks post-treatment.

6.2, 6.7, 6.8 Statistical Design, Power, Analysis plan, & Missing data.

An intent-to-treat analysis is planned. Before carrying out inferential statistical procedures, exploratory data analysis will be performed: all variable distributions will be examined and descriptive summary statistics will be provided: including means, standard deviations, and ranges for continuous variables, as well as percentages and frequencies for categorical variables, will be provided to describe the study sample. Variable transformations will be made in cases where distributions are skewed, or otherwise fail to meet the assumptions for analyses; nonparametric procedures will be used where transformations would be inappropriate. Plots will be used to describe the data and identify outliers and influential observations.

Aim 1

Analysis. The primary analysis for Aim 1 will be to compare the control and CG intervention arms with respect to CG anxiety at T4 (20 weeks postradiation treatment). A linear mixed model repeated measures analysis will be used to obtain mean changes from baseline in anxiety scores at Times T2, T3, and T4, using baseline anxiety as a covariate, also adjusting for covariates described in Table 4. A contrast of means will be constructed to compare arms with respect to change in anxiety at T4 (primary analysis) at the 0.05 significance level. In addition, the baseline characteristics of the two treatment groups will be compared using appropriate 2-sample tests for continuous or binary outcomes, and in a secondary analysis, characteristics found to differ between groups at baseline will be adjusted for in the linear mixed model. A secondary analysis will test for differences between groups at the other postbaseline time points, using the Tukey method to control the familywise error rate on a per outcome basis. Other CG outcomes will be compared between groups using a similar approach.

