(2) For model development and validation proposed in above aims, we will follow the general statistical model building strategy documented in detail in Harrell.¹¹³ Some major aspects we will consider are: (a) dealing with missing data by multiple imputing of missing predictor values to make good use of partial subject information, (b) allowing for nonlinear predictor effects using regression splines, (c) adjusting the variance-covariance matrix for multiple imputation, (d) graphically interpreting the model using partial effect plots and nomograms, (e) quantifying the clinical utility (discrimination ability) of the model, and (f) internally validating the calibration and discrimination of the model using the bootstrap to estimate the model's likely performance on a new observation of samples from the same sample stream.

6.3 Stratification factors and intervention allocation plan for randomized studies.

Randomization will be done using the minimization stratified randomization technique (QMinim). Minimization is designed to balance pre-identified stratifying covariates across treatment assignments more effectively than simple randomization.⁸⁷⁻⁸⁹ The covariates will be CG gender, CG age, and patient cancer type.

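### The primary mixed model does not list the three factors used to minimise allocation (caregiver gender, caregiver age, patient cancer type), so the test is conservative if they are prognostic

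*Combined protocol and SAP*

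**What the plan says.** **Allocation.** Sections 4.0 and 6.3 both describe minimisation. Section 6.3 names the factors: "The covariates will be CG gender, CG age, and patient cancer type".

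**Primary model.** Section 6, Aim 1, specifies a linear mixed model for change in caregiver anxiety at T2, T3 and T4, "using baseline anxiety as a covariate, also adjusting for covariates described in Table 4". The individual terms are not listed there.

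**Table 4 (Section 5.4).** In the block of moderators and covariates, the demographic row reads "Demographic characteristics (race, marital status, employment status, health insurance, socioeconomic status" and closes there, without age or gender. The illness row reads "Patient Illness Factors (Stage; time since diagnosis; treatment type, e.g., concurrent chemotherapy; HPV status in HNC and anal cancer" and closes there, without cancer type. The remaining rows cover palliative care, performance status, care demands, mental health interventions, financial toxicity and social support. The three factors appear only in the note under the table: "CG age, CG gender, and PT cancer type will be used in the minimization stratified randomization technique". The separate account of covariates in Section 1.2 (Theoretical Framework) omits all three as well.

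**Secondary analysis.** In Aim 1, "characteristics found to differ between groups at baseline will be adjusted for in the linear mixed model".

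**The concern.** Minimisation makes the arms alike on the chosen factors, so the part of the outcome variance that those factors explain largely drops out of the difference between arms. A model without the factors does not know this. It leaves that variance in the residual and reports a standard error larger than the estimate's true variability under the allocation. The test then rejects a true null hypothesis less often than 5%, the interval is wider than it need be, and the balance that the design obtained is not turned into precision.

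The secondary rule is a poor safety net. It brings in characteristics that turn out unbalanced, and the minimised factors are the ones least likely to do so.

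The plan itself gives reason to expect cancer type to matter: Section 1.2 describes different toxicities and symptom courses for each diagnosis. It gives no figure for how strongly any of the three factors predicts caregiver anxiety.

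**Working it through.** **The plan's own figure.** Section 6, Aim 1 Power: 81 per arm, two-sided 0.05, 80% power, baseline-to-T4 correlation 0.50, detectable difference 0.36 SD (0.41 SD without baseline adjustment). The residual SD is √(1 − 0.50²) = 0.866, and the detectable difference is (1.960 + 0.842) × 0.866 × √(2/n).

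- n = 81: 0.381 SD (0.440 unadjusted). The stated 0.36 is not reproduced.
- n = 90, i.e. all 180 randomised with no dropout: 0.362 SD (0.418 unadjusted). This matches 0.36.
- n = 107, the extension's 214 analysed: 0.332 SD.

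That mismatch is a separate matter. It is relevant here because the planned power credits adjustment for baseline anxiety and nothing else. The steps below start from a nominal 80%, so they do not depend on it.

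**Set-up.** Let R² be the share of residual variance that the three factors explain beyond the terms already in the model. The documents do not give it, so 5%, 10% and 15% are assumed. Take the limiting case in which allocation balances the factors perfectly. The true SE of the treatment contrast is then √(1 − R²) times the SE that the model without the factors reports.

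**Formulas.**
- Type I error without the factors: 2 × [1 − Φ(1.960/√(1 − R²))].
- Power without the factors: Φ(0.842/√(1 − R²)). This is above 80% because the estimate is already less variable.
- Power with the factors: Φ(2.802/√(1 − R²) − 1.960).

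| R² | √(1 − R²) | Type I error, factors omitted | Power, omitted | Power, included | Forgone |
|---|---|---|---|---|---|
| 0.05 | 0.975 | 0.0443 | 80.6% | 82.0% | 1.4 points |
| 0.10 | 0.949 | 0.0388 | 81.2% | 84.0% | 2.7 points |
| 0.15 | 0.922 | 0.0335 | 81.9% | 86.0% | 4.0 points |

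At R² = 0.02 the same formulas give a type I error of 0.048 and about 0.5 points forgone. At R² = 0 nothing is lost.

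**Check without perfect balance.** Minimisation on three factors was simulated with a biased coin of 0.8, assumed level frequencies and equal contributions from the factors. A single-time-point ANCOVA with baseline stood in for the repeated-measures model (2,500 runs per scenario, true effect 0.36 SD for power). Monte Carlo error is about 0.4 points for type I error and up to about 0.9 for power.

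| N | R² | Type I error, omitted v included | Power, omitted v included |
|---|---|---|---|
| 162 | 0 | 4.5% v 4.7% | 74.3% v 74.0% |
| 162 | 0.05 | 4.4% v 4.8% | 76.1% v 77.2% |
| 162 | 0.10 | 4.2% v 5.0% | 75.7% v 78.5% |
| 162 | 0.20 | 2.8% v 4.7% | 76.2% v 83.2% |
| 214 | 0.05 | 5.2% v 5.7% | 85.3% v 86.2% |
| 214 | 0.10 | 3.8% v 5.4% | 85.1% v 87.2% |
| 214 | 0.20 | 3.0% v 4.7% | 88.2% v 92.2% |

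Direction and size agree with the formulas. At 5% the type I effect is within simulation error; by 20% it is clear.

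**The case against.** **The factors may be meant to be in the model.** The Aim 1 text points to Table 4, the note to that table names all three, and Section 6.3 calls them covariates. No sentence excludes them. This stands as far as it goes: a reader might infer that the plan rules the factors out, and the documents do not support that. But the note gives them an allocation role only, and both covariate lists omit them, so omission remains the more natural reading.

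**The size is assumed.** This stands. R² is what remains after baseline anxiety and the Table 4 covariates, some of which overlap with the factors; HPV status, for example, applies only to head and neck and anal cancers. The true share could be close to zero.

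**The power gain is easily overstated.** A reader might compare 82%, 84% and 86% with the nominal 80% and infer gains of 2, 4 and 6 points. That ignores the power that minimisation already adds to the test without the factors. The consistent comparison gives 1.4, 2.7 and 4.0.

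**Recruiting site.** Recruitment covers "Radiation Therapy Departments of the Seidman Cancer Center at the University Hospitals main campus, satellite community facilities, and MetroHealth Cancer Center", and Section 3.0 adds that "The extension period will include family CGs and patients recruited from MetroHealth". Site is in neither the minimisation nor the listed covariates, and a reader might fold it into this point. The argument does not reach it: allocation did not balance site, so leaving it out does not make the SE too wide in this way. It could matter only as an ordinary prognostic covariate. The documents give no evidence that it predicts caregiver anxiety, and race, insurance, employment and socioeconomic status are already listed. In the simulation at N = 162, a site term with no effect on outcome cost 0.3 to 1.6 points of power.

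**Harm to the trial.** A reader might also infer an invalid test or an underpowered trial. The error is on the conservative side, and the sample size calculation claims no benefit from these factors.

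**Conclusion.** The point holds as a modest, almost free improvement. As written, the primary model does not list the factors on which allocation is minimised, and the secondary rule would tend not to pick them up. If the factors are prognostic beyond the other terms, the primary test is conservative and some precision is given away, by the amounts tabulated above for assumed shares of 5% to 15%. Those type I figures are a limiting case, since real minimisation balances less than perfectly. The conclusion rests on the natural reading of Table 4 and on a prognostic strength that the documents do not state. It does not bear on the trial's validity, does not put power below the planned calculation, and does not extend to site.

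**What to change.** In Section 6, Aim 1, state that the primary mixed model includes caregiver age (continuous), caregiver gender and patient cancer type as fixed baseline covariates alongside baseline anxiety. Use the same terms in the mixed models for the other caregiver outcomes and for patient HRQOL. Adding the three factors to the covariate rows of Table 4 would remove the remaining ambiguity.

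The cost is one sentence. Allocation already requires all three variables. With five cancer types the terms use 4 + 1 + 1 = 6 degrees of freedom, which is small against 162 or 214 analysed caregivers; in the simulation, adding the factors when they had no effect moved power by 0.3 points or less.

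Do not require the full set in the count models for Aim 2. The plan expects a control mean of 0.25 unplanned admissions: 0.25 × 81 ≈ 20 events in the control arm and, at the stated 72% reduction, 0.25 × 0.28 × 81 ≈ 6 in the intervention arm. Six extra terms on about 26 events is too many.

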8.0 APPENDICES

Appendix A. Instruments (attached)

Appendix B. Study brochure for caregivers
